Name: v2\_Supporting Literature

## Study Procedures

**If you uploaded a separate research protocol document in the 'Research Protocol' page, cite the applicable section and page numbers from that document in the answer boxes below. If some of the questions below are not applicable to the research (i.e., chart review), enter "N/A."**

1 \*Describe all procedures being performed for research purposes only (these procedures would not be done if individuals were not in the study) and when they are performed, including procedures being performed to monitor subjects for safety or to minimize risks:

The study is a 12-week, double-blind, placebo-controlled, randomized clinical trial of the efficacy of anti-inflammatory combination therapy for the treatment of people with schizophrenia, who present with persistent positive symptoms.

All participants will be of either gender and of any race, with an age range of 18 - 60. Participants will meet DSM-IV -TR criteria for schizophrenia or schizoaffective disorder. SCID assessment will be administered as needed to determine this criterion. Participants must be judged competent to participate in the informed consent process and provide voluntary informed consent.

For all patients, recruitment will occur as detailed in the recruitment section. Consenting and research activity will thereafter be conducted at MPRC.

Evaluation Phase: There will be a 4-week Evaluation Phase during which baseline symptoms, safety, laboratory, and neuropsychological assessments will be collected.

Treatment Phase: Participants who continue to fulfill entry criteria will be entered into the 12-week Double-blind Treatment Phase, in which participants will be randomly assigned to salsalate, fluvastatin, and omega-3-fatty acid combination therapy (n=30) or placebo (n=30) using a permuted block randomization system. Treatment assignment order is random within each block, with an equal number of participants assigned to each treatment. The block sizes will vary in random sequence between 2 and 4. The salsalate target dose will be 4 gm/day, administered in two divided doses of 2 gm in the morning and 2 gm in the evening. The fluvastatin target dose will be 40 mg/day. Participants randomized to fluvastatin will receive placebo fluvastatin in the morning and active drug in the evening. We selected fluvastatin (because it does not interfere with the metabolism of risperidone and paliperidone (two widely used antipsychotics), and it crosses the blood brain barrier. We will use a combined omega-3-fatty acid preparation of EPA and DHA in a 1gm capsule. Each 1gm capsule will contain 180.9mg of EPA and 120.6mg of DHA in doses of two capsules in the morning and two capsules in the evening (2g omega-3-fatty acid in the morning and 2g omega-3-fatty acid in the evening).

evening). We selected this dose of EP A and DHA, because these were the doses used in the Amminger et al. study ( No. 48, Summary of Supporting Literature section), which has, to date, produced the most profound results for this intervention.

Assessments: We will collect the following clinical, neuropsychological, safety, and laboratory assessments:

A. Clinical:

- 1) Brief Psychiatric Rating Scale (BPRS; Overall & Gorham, 1980): A 20-item scale of psychiatric symptoms rated from 1 (not present) to 7 (very severe).
- 2) Scale for the Assessment of Negative Symptoms (SANS): A 22-item scale designed to quantify the severity of negative symptoms in schizophrenia. Items are rated from 0 (not present) to 5 (severe).
- 3) Calgary Depression Scale (CDS): the CDS total score will be used to measure depressive symptoms. The CDS was specifically designed to assess depressive symptoms in people with schizophrenia.
- 4) CGI-Severity of illness (CGI-S): the CGI-S will be used to assess global changes.
- 5) Fagerstrom Test for Nicotine Dependency (FTND): the FTND will be used to document smoking status and to measure change in smoking status during the course of treatment.
- 6) Columbia Suicide Severity Rating Scale (C-SSRS): The C-SSRS is a questionnaire used for suicide assessment at screening and during the course of treatment.

The primary evaluators will administer the BPRS, SANS, Calgary Depression Scale (CDS) and CGI-S at the beginning of the Evaluation Phase and bi-weekly thereafter. The FTND will be administered at the beginning and end of the Treatment Phase.

B. Neuropsychological Assessments: The MATRICS Consensus Cognitive Battery (MCCB) will be used to assess neuropsychological test performance. All participants will receive this portion of the assessments at MPRC.

C. Side Effects: Side Effect Checklist (SEC); the SEC is designed to assess vital signs and commonly occurring medication-related side effects. EKG and Vital Signs will also be monitored. At MPRC, the Side-Effect Checklist (SEC) and vital signs will be administered at treatment baseline and bi-weekly thereafter by a non-blind clinical pharmacist, who will not disclose the results to treatment/rating clinicians.

D. Laboratory: All patients will receive these assessments at MPRC. If laboratory abnormalities occur, repeat labs may be performed on visits where they are unscheduled in the assessment schedule. This will be determined by a study physician.

- 1) Safety: CBC; complete metabolic panel (CMP), including electrolytes, BUN, creatinine, fasting blood glucose, liver function tests, and lipid profile; U/A; pregnancy test; vital signs.
- 2) Cytokine profile: IL-1 $\beta$ , IL-1RA, IL-2, sIL-2R, IL-6, IL-10, IL-12, IL-17, CRP, IFN- $\gamma$ , TNF- $\alpha$ , and TGF- $\beta$ .

E. Other: We will collect blood for peripheral blood mononuclear cells (PBMC) cultures, which will be used to evaluate in vitro lipopolysaccharide-induced cytokine production. The use of PBMC cultures complements the collection of peripheral cytokine measures. The latter may be vulnerable to differential concentrations between the site of cytokine release and blood concentrations and the relatively short half-life of cytokines.

- 2 \* Describe all procedures already being performed for diagnostic or treatment purposes (if not applicable to the study, enter "N/A"):

The procedures in this protocol are conducted for research purposes.

- 3 \* Describe the duration of an individual participant's participation in the study:

There will be a 4-week evaluation phase during which baseline symptom, safety, laboratory, and neuropsychological assessments will be collected. Participants who continue to fulfill entry criteria will be entered into the 12-week Double-blind Treatment Phase. Hence entire duration of participation for the participant is 16 weeks.

- 4 \* Describe the duration of the entire study:

We anticipate that the duration of this study will be three years.

- 5 \* Describe any additional participant requirements:

None

ID: VIEW4E0280585B40  
Name: v2\_Study Procedure

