### 1 \* Describe the purpose, specific aims, or objectives of this research. State the hypothesis to be tested:

Primary Aims:

1. To determine if adjunctive anti-inflammatory combination therapy is superior to placebo for persistent positive symptoms.
2. To determine if adjunctive anti-inflammatory combination therapy is superior to placebo for depressive and negative symptoms.

Secondary Aims:

1. To determine if adjunctive anti-inflammatory combination therapy compared to placebo is associated with increased incidence of side effects.
2. To determine if adjunctive anti-inflammatory combination therapy is superior to placebo for depressive and negative symptoms.
3. To determine if adjunctive anti-inflammatory combination therapy compared to placebo is associated with an improvement in the pro-inflammatory cytokines: interleukin (IL)-1 $\beta$ , IL-6, and Tumor Necrosis Factor (TNF)- $\alpha$ .

We hypothesize adjunctive anti-inflammatory combination therapy will be associated with improvements in depressive and negative symptoms and a reduction in pro-inflammatory cytokines. We hypothesize that no elevated adverse risk will be associated with adjunctive anti-inflammatory combination therapy relative to placebo.

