## Sample Size and Data Analysis

**If you uploaded a separate research protocol document in the 'Research Protocol' page, cite the applicable section and page numbers from that document in the answer boxes below.**

- 1 \* Provide the rationale and sample size calculations for the proposed target population:

Power for analyses:

Specific Aim 1: Based on similar MPRC studies of adjunctive treatments, we anticipate approximately a 10% dropout rate. In previous trials of similar length, we have found that the correlation,  $r$ , between baseline and follow-up scores is approximately  $r=0.6$ . The effect size,  $d/\sigma$ , detectable from this study can be estimated from the formula  $(d/\sigma)^2 = 2(\alpha + z\beta)^2(1-r^2)/n$ , where  $d$  is the MM-ANCOVA difference estimate at week 8,  $\sigma$  the standard deviation at week 8,  $z\beta = 0.84$  and  $\alpha = 1.96$  are the standard normal percentiles corresponding to power=0.80 and  $\alpha=0.05$  (two-sided). We would have power to detect an effect size:  $d=0.61$ .

Specific Aim 2: The correlation,  $r$ , between baseline and follow-up MCCB composite scores has now been reported in multiple clinical trials to be  $r>0.9$ . Substituting this value for  $r$  into the ANCOVA power formula given above, we should have power=0.80 to detect an effect size:  $d=0.33$  on the MCCB total score.

- 2 \* Provide the plan for data analysis. Include in the description the types of comparisons that are planned (e.g., comparison of means, comparison of proportions, regressions, analysis of variance, etc.), which is the primary comparison/analysis, and how the analyses proposed will relate to the primary purposes of the study:

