Specific Aim #1: The effect of combined anti-inflammatory treatment versus placebo on persistent positive symptoms will be tested using the mixed model for repeated measures analysis of covariance (MM-ANCOVA): follow-up score = baseline score + study week + treatment x study week, where "study week" represents a set of binary indicators of whether the follow-up measurement comes from weeks 2, 4, 6, or 8; the main effect of treatment in this model is the average (across weeks 2, 4, 6, and 8) adjusted (for baseline score) difference in follow-up scores between anti-inflammatory treatment and placebo, while the treatment x week interaction tests for significant variation among follow-up weeks in the magnitude of the treatment effects. The primary outcome tested from this model will be a post hoc estimate of the treatment difference at week 8; exploratory analysis of the average treatment effect across weeks and changes in the magnitude of the treatment effect over time will also be conducted.

Specific Aim #2: The primary test for treatment effects on cognition will be performed using the MCCB composite score and the ANCOV A model follow-up composite score = baseline composite score + treatment. Exploratory analyses examining treatment effects for specific domains will be analyzed using the MM-ANCOV A model: follow-up domain T -score = baseline domain T -score + domain + treatment x domain, where the treatment x domain interaction term provides an overall test for variation in the magnitude of anti-inflammatory - placebo T -differences across domains, and the effects of anti-inflammatory treatments in specific domains can be estimated by post-hoc tests from this general model.

Secondary outcomes:

- 1) Treatment differences on clinical symptom outcomes (CDS depression, SANS negative symptom score) will be assessed with MM-ANCOV A, using models similar to that prescribed for analyses of positive symptoms.
- 2) Treatment differences on side effects will be assessed by comparing the proportion of participants in each group with either new onset or worsening compared to baseline for each of a list of specified side effects, using Fisher's exact test.

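### The hypothesis of no added side-effect risk is tested only for a difference, with no interval or margin; at 30 per arm a non-significant result cannot support it

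*Combined protocol and SAP*

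**What the plan says.** Under Justification, Objective, & Research Design (item 1), Secondary Aim 1 asks whether the combination "compared to placebo is associated with increased incidence of side effects". The hypothesis attached to the aims is one of no excess: "We hypothesize that no elevated adverse risk will be associated with adjunctive anti-inflammatory combination therapy relative to placebo".

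Under Sample Size and Data Analysis (item 2, secondary outcome 2), the analysis consists of "comparing the proportion of participants in each group with either new onset or worsening compared to baseline". It is run separately "for each of a list of specified side effects, using Fisher's exact test". No interval, margin, expected rate, power or rule of interpretation is given for side effects. Item 1 of the same section gives power for the two efficacy aims only.

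Under Study Procedures (item 1, C. Side Effects), vital signs and the Side Effect Checklist "will be administered at treatment baseline and bi-weekly thereafter by a non-blind clinical pharmacist, who will not disclose the results to treatment/rating clinicians". The trial is described as double-blind.

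**The concern.** There are two problems, and they add to each other.

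First, the hypothesis and the test point in opposite directions. A test of difference can give evidence that an excess exists. Failing to find one says little unless the study could have found it, and nothing in the plan shows that it could. With an interval, a reader would see how large an excess remains possible. With a p-value alone, the reader would not.

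Second, the compared outcome is new onset or worsening of symptoms such as tinnitus, headache, nausea and myalgia. The person who administers the questions knows the allocation. For symptoms of this kind, how a question is put and followed up can affect the answer.

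At stake is the safety conclusion for a three-drug adjunct. If the tests came out non-significant and the hypothesis were declared supported, substantial excesses would still be compatible with the data.

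**Working it through.** **Inputs from the documents**
- Allocation: "combination therapy (n=30) or placebo (n=30) using a permuted block randomization system" (Study Procedures).
- Dropout: "we anticipate approximately a 10% dropout rate" (Sample Size and Data Analysis, item 1), so 30 × 0.9 = 27 per arm. The analysis set for the Fisher tests is not stated, so both sizes are shown.
- Level: two-sided 0.05 is stated for the efficacy power. It is assumed here for the Fisher tests, for which no level is given.

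**Inputs that are assumed**
- Side-effect rates per arm. The documents give none. The 25% under Monitoring Plan - Internal DSMB (item 4) is an incidence at which the board notifies the principal investigator. It is not a design rate.

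**Step 1. Reproduce the plan's own figure.** The plan uses d = √[2(1.96 + 0.84)²(1 − r²)/n]. With r = 0.6 and n = 27, d = √[2 × 7.84 × 0.64 / 27] = 0.61, as stated. With n = 30 it would be 0.58. The plan's power therefore rests on 27 per arm, and it covers efficacy only.

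**Step 2. Exact power of the Fisher test.** Power = Σ Bin(a; n, p₁) · Bin(b; n, p₀) over all pairs (a, b) with two-sided Fisher p ≤ 0.05.

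| Placebo vs active (assumed) | 30 per arm | 27 per arm |
|---|---|---|
| 10% vs 20% | 10% | 8% |
| 10% vs 25% | 21% | 17% |
| 15% vs 30% | 19% | 16% |
| 5% vs 25% | 44% | 36% |
| 10% vs 40% | 71% | 63% |

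With a 10% placebo rate, 80% power needs an active rate of about 44% (30 per arm) or 46% (27 per arm). The test is also conservative for uncommon events: with both true rates at 10%, it rejects only 0.9% (30 per arm) or 0.7% (27 per arm) of the time.

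**Step 3. What a non-significant result leaves open.** Take 7/30 on active and 3/30 on placebo. Fisher p = 0.30 and the difference is 0.233 − 0.100 = 0.133. The Wilson limits are 0.118 to 0.409 and 0.035 to 0.256. The Newcombe limits are:
- lower: 0.133 − √[(0.233 − 0.118)² + (0.256 − 0.100)²] = −0.06
- upper: 0.133 + √[(0.409 − 0.233)² + (0.100 − 0.035)²] = +0.32

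An excess of up to 32 points is not excluded. At 10/30 against 3/30, Fisher's test is still non-significant (p = 0.057), while the Newcombe interval is +2 to +42 points.

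**Step 4. Best case.** If the observed rates are equal, the simple 95% half-width is 1.96√[2p(1 − p)/n]. At p = 10% this is ±15 points (30 per arm) or ±16 (27 per arm). At p = 20% it is ±20 or ±21. For scale, excluding a 10-point excess at a common 10% rate, with one-sided 0.025 and 80% power, needs (1.96 + 0.84)² × 2 × 0.1 × 0.9 / 0.1², about 142 per arm. That margin is illustrative and is not in the plan.

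**The case against.** **The aim itself is worded as a question of difference.** Secondary Aim 1 asks whether side effects increase, and Fisher's test addresses that. This is fair. The mismatch lies with the hypothesis sentence, not with the aim.

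**Power has no single value.** A reader might conclude that the safety comparison has about 20% power. The documents do not support that as a property of the plan. It is what an assumed 15-point excess gives; other assumptions give 8% to 71% in the table above.

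**No misreading is planned.** A reader might also infer that the sponsor will present non-significance as reassurance. No section says how such a result will be interpreted. The plan's silence on this is what can be criticised.

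**The unblinded pharmacist has a purpose.** Withholding checklist results from treating and rating clinicians appears designed to keep revealing symptoms such as tinnitus away from the efficacy raters. That stands. The text says the checklist is administered by the pharmacist, not that the pharmacist scores it, and the form is an attachment not reproduced here. The size and direction of any bias are therefore unknown. Giving the task to a unit nurse could weaken the firewall, since nurses may belong to the treatment staff from whom results are withheld.

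**Safety does not rest on the checklist alone.** EKG, laboratory tests, the C-SSRS, SAE reporting and DSMB review are all in place. The point concerns only the planned between-arm comparison of side effects; no between-arm analysis is specified for the other measures.

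**Conclusion.** The concern holds in a limited form. The hypothesis of no elevated adverse risk has no analysis that could support it: the planned tests are for a difference, with no interval and no margin, at 27 to 30 per arm. Under the assumed rates, a rise from 10% to 20% would be missed at least nine times in ten, and a rise from 10% to 25% about four times in five. Even equal observed rates of 10% would leave about ±15 points. These figures assume two-sided 0.05 and illustrative event rates, because the documents supply neither for this analysis. The conclusion does not depend on a particular rate.

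The side-effect comparison is also not assessor-blind. That is a limitation to disclose, with unknown direction; it does not show that the result will be biased. The matter concerns a secondary aim and does not affect the efficacy analyses.

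**What to change.** 1. **Sample Size and Data Analysis, secondary outcome 2.** For each listed side effect, report the number and proportion per arm and the risk difference with a Newcombe 95% interval, alongside Fisher's test. State the analysis set. Say in advance that the interval carries the interpretation, because the two methods can disagree near the boundary (as with 10/30 against 3/30).
2. **Hypothesis statement.** Restate it as estimation of the difference in side-effect incidence, and add that a non-significant test will not be taken as absence of added risk.
3. **Assessor.** State that the side-effect comparison is not assessor-blind and that any bias is of unknown direction. Participant self-completion, with the form passed to the pharmacist, is an option only if results still stay away from treating and rating clinicians. Funding Information refers to the final two participants, so enrolment may be nearly complete. A change of collection method at that stage would mix two kinds of ascertainment.
4. **Reconcile the sections.** Study Procedures has the checklist bi-weekly with results not disclosed to treating clinicians. Research Related Risks has it weekly and links some of the listed side effects to management actions. These passages must be brought into agreement, because the number of assessments also affects how often new onset or worsening is recorded.

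Items 1 and 2 need no extra participants, visits or data. Their price is a less favourable safety statement: the report could say only how large an excess remains possible.

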## Sample Size and Data Analysis

**If you uploaded a separate research protocol document in the 'Research Protocol' page, cite the applicable section and page numbers from that document in the answer boxes below.**

- 1 \* Provide the rationale and sample size calculations for the proposed target population:

Power for analyses:

Specific Aim 1: Based on similar MPRC studies of adjunctive treatments, we anticipate approximately a 10% dropout rate. In previous trials of similar length, we have found that the correlation,  $r$ , between baseline and follow-up scores is approximately  $r=0.6$ . The effect size,  $d/\sigma$ , detectable from this study can be estimated from the formula  $(d/\sigma)^2 = 2(\alpha + z\beta)^2(1-r^2)/n$ , where  $d$  is the MM-ANCOVA difference estimate at week 8,  $\sigma$  the standard deviation at week 8,  $z\beta = 0.84$  and  $\alpha = 1.96$  are the standard normal percentiles corresponding to power=0.80 and  $\alpha=0.05$  (two-sided). We would have power to detect an effect size:  $d=0.61$ .

Specific Aim 2: The correlation,  $r$ , between baseline and follow-up MCCB composite scores has now been reported in multiple clinical trials to be  $r>0.9$ . Substituting this value for  $r$  into the ANCOVA power formula given above, we should have power=0.80 to detect an effect size:  $d=0.33$  on the MCCB total score.

- 2 \* Provide the plan for data analysis. Include in the description the types of comparisons that are planned (e.g., comparison of means, comparison of proportions, regressions, analysis of variance, etc.), which is the primary comparison/analysis, and how the analyses proposed will relate to the primary purposes of the study:

Specific Aim #1: The effect of combined anti-inflammatory treatment versus placebo on persistent positive symptoms will be tested using the mixed model for repeated measures analysis of covariance (MM-ANCOVA): follow-up score = baseline score + study week + treatment x study week, where "study week" represents a set of binary indicators of whether the follow-up measurement comes from weeks 2, 4, 6, or 8; the main effect of treatment in this model is the average (across weeks 2, 4, 6, and 8) adjusted (for baseline score) difference in follow-up scores between anti-inflammatory treatment and placebo, while the treatment x week interaction tests for significant variation among follow-up weeks in the magnitude of the treatment effects. The primary outcome tested from this model will be a post hoc estimate of the treatment difference at week 8; exploratory analysis of the average treatment effect across weeks and changes in the magnitude of the treatment effect over time will also be conducted.

Specific Aim #2: The primary test for treatment effects on cognition will be performed using the MCCB composite score and the ANCOV A model follow-up composite score = baseline composite score + treatment. Exploratory analyses examining treatment effects for specific domains will be analyzed using the MM-ANCOV A model: follow-up domain T -score = baseline domain T -score + domain + treatment x domain, where the treatment x domain interaction term provides an overall test for variation in the magnitude of anti-inflammatory - placebo T -differences across domains, and the effects of anti-inflammatory treatments in specific domains can be estimated by post-hoc tests from this general model.

Secondary outcomes:

- 1) Treatment differences on clinical symptom outcomes (CDS depression, SANS negative symptom score) will be assessed with MM-ANCOV A, using models similar to that prescribed for analyses of positive symptoms.
- 2) Treatment differences on side effects will be assessed by comparing the proportion of participants in each group with either new onset or worsening compared to baseline for each of a list of specified side effects, using Fisher's exact test.
- 3) Treatment differences in changes in cytokine expression will be assessed using the Wilcoxon rank sum test to compare change scores on each cytokine measure. We anticipate many participants will have cytokine measurements below the limit of detection at one or both visits. For such participants, we will impute cytokine measurements equal to ½ the limit of detection for the assay.
- 4) Spearman rank correlations will be assessed between changes in symptoms and cognitive outcomes

ID: VIEW4E0280605280  
Name: v2\_Sample Size and Data Analysis

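### The Aim 1 repeated-measures model and the Aim 2 domain model are printed without a treatment main effect, so the exploratory interaction tests, fitted as printed, would not test variation across weeks or domains

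*Combined protocol and SAP*

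**What the plan says.** Sample Size and Data Analysis, item 2, Specific Aim #1 gives the model as "follow-up score = baseline score + study week + treatment x study week", with study week entered as binary indicators for weeks 2, 4, 6 and 8. It then says that "the main effect of treatment in this model is the average (across weeks 2, 4, 6, and 8) adjusted (for baseline score) difference" between the arms, and that "the treatment x week interaction tests for significant variation among follow-up weeks in the magnitude of the treatment effects". The test that counts is set out next: "The primary outcome tested from this model will be a post hoc estimate of the treatment difference at week 8". The average effect and the change in effect over time are labelled exploratory.

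Specific Aim #2 uses two models. The primary one, for the MCCB composite, is baseline plus treatment, so treatment is written out. The exploratory domain model has baseline, domain and treatment x domain, with no treatment term. The plan says of it that "the treatment x domain interaction term provides an overall test for variation in the magnitude of anti-inflammatory" minus placebo differences across domains. Domain-specific effects are to come from post-hoc tests in that model.

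Under Secondary outcomes, CDS and SANS are to be analysed with models similar to the one for positive symptoms.

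Study Procedures, item 1, has the symptom scales rated "at the beginning of the Evaluation Phase and bi-weekly thereafter", and the Evaluation Phase lasts 4 weeks. The analysis section refers only to a baseline score and does not say which rating or ratings it means.

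**The concern.** Equation and prose do not describe the same model. The prose needs a treatment main effect and an interaction that measures departures from it. The equation has neither: without the main effect, treatment x week absorbs the whole treatment effect, one parameter per week. A standard test of that term asks whether there is any effect at any week. A treatment that works equally well at every visit would usually produce a significant result, and under the plan's wording that result would be read as an effect that changes over time. The domain model behaves the same way: a uniform benefit across cognitive domains would be reported as domain-specific.

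Simply adding the treatment term leaves one loose end. With reference-coded week indicators, the raw treatment coefficient is the effect at the reference week. It equals the average only under sum-to-zero coding, or if the average is requested as a contrast.

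A smaller matter is the covariate of the primary test. The schedule implies two or three symptom ratings before treatment starts, and the plan does not say how they become one baseline score.

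**Working it through.** **Inputs from the plan.** 30 randomised per arm (Study Procedures). Also 10% dropout, r = 0.6 between baseline and follow-up, two-sided alpha 0.05 and power 0.80 (Sample Size and Data Analysis, item 1). Hence n = 30 x 0.9 = 27 per arm. Four follow-up weeks are used, as printed in the model.

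**Assumed.** Equal correlation rho between follow-up ratings, 0.6 to 0.8. The plan gives no value.

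**1. The plan's own figure.** Detectable effect = sqrt[2(1.96 + 0.84)^2 (1 - r^2)/n] = sqrt[2 x 7.84 x 0.64/27] = 0.610. The stated 0.61 reproduces. With r = 0.9 the same formula gives 0.332, matching the stated 0.33 for Aim 2.

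**2. What the printed term tests.** Let d2, d4, d6, d8 be the weekly treatment differences.
- As printed, treatment x week = 0 means d2 = d4 = d6 = d8 = 0: 4 df.
- Variation between weeks needs the null d2 = d4 = d6 = d8: 3 df.

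**3. Rejection rate when the effect is constant at d = 0.61 SD.** After baseline adjustment, each weekly difference has variance (2/n)(1 - r^2) and each pair has covariance (2/n)(rho - r^2). For a constant effect the noncentrality of the 4-df test is

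lambda = 4d^2 / {(2/n)[(1 - r^2) + 3(rho - r^2)]}.

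At rho = 0.6: 4 x 0.3721 / [(2/27)(0.64 + 3 x 0.24)] = 1.4884/0.1007 = 14.8.

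| rho | lambda | 4 df, chi-square | 4 df, F (about 51 denominator df) | 3 df (correct) |
|---|---|---|---|---|
| 0.6 | 14.8 | 0.89 | 0.85 | 0.05 |
| 0.7 | 12.1 | 0.81 | 0.76 | 0.05 |
| 0.8 | 10.3 | 0.73 | 0.68 | 0.05 |

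The 3-df test has noncentrality 0 here, so it rejects at its nominal level. For a constant effect of 0.3 SD, the 4-df chi-square test rejects 29% (rho = 0.6) to 21% (rho = 0.8) of the time.

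**4. Simulation.** With 2,000 runs at rho = 0.7 and known covariance:
- Constant 0.61 SD effect: the 4-df test rejected in 0.776 of runs, the 3-df test in 0.047 and the week 8 contrast in 0.791.
- No effect: 0.055, 0.052 and 0.053.

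The 0.776 is a little below the formula's 0.81, which ignores chance baseline imbalance. The conclusion is the same.

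**5. What does not change.** Week plus treatment x week spans the same set of means as week plus treatment plus treatment x week. The fitted weekly differences are therefore identical in the two forms. The week 8 contrast, its type I error, the 0.61 SD and each single-domain contrast stay as they are. The average (d2 + d4 + d6 + d8)/4 is also estimable from either form.

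**6. Baseline definition.** If k ratings, each correlating 0.6 with follow-up and rho_b with one another, are averaged, the mean correlates r_k = 0.6/sqrt{[1 + (k - 1)rho_b]/k} with follow-up. Putting r_k into the plan's formula with n = 27:

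| k | rho_b (assumed) | r_k | detectable effect | power at 0.61 |
|---|---|---|---|---|
| 1 | - | 0.60 | 0.61 | 80% |
| 2 | 0.6 | 0.67 | 0.57 | 86% |
| 2 | 0.9 | 0.62 | 0.60 | 81% |
| 3 | 0.6 | 0.70 | 0.54 | 88% |
| 3 | 0.8 | 0.64 | 0.58 | 83% |
| 3 | 0.9 | 0.62 | 0.60 | 82% |

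The table assumes that all ratings predict follow-up equally well. If three ratings instead correlate 0.50, 0.55 and 0.60 with follow-up and 0.8 with one another, the mean correlates 0.55/sqrt(2.6/3) = 0.59, slightly below the 0.60 of the best single rating. There is then no gain.

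**The case against.** The strongest defence is that the prose already names the right targets: an average over weeks and a test of variation between weeks. The equation may be shorthand in which the main effect is understood. An analyst who works from the definitions will add the term, or request the equality contrast, and get correct results. That stands as far as it goes: a wrong test is a risk, not a certainty. But shorthand is not a safe assumption, because the MCCB composite model in the next paragraph does write the treatment term out, while both interaction models omit it.

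The second defence is that nothing confirmatory depends on this. That is correct. A reader might infer from a fault in the Aim 1 equation that the primary test or its power is compromised. The documents do not support this: the primary test is the week 8 difference, which is the same in both forms. Nor would the domain-specific estimates be wrong, or the average effect undefined; both can be obtained as contrasts from the printed model.

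A reader might also infer that the plan adjusts for a single baseline rating and so gives up precision. It does not say that. It leaves the baseline score undefined, and collecting baseline symptoms over a 4-week phase is compatible with averaging. The number of pre-treatment ratings is itself inferred, since the assessment schedule is a separate attachment. BPRS thresholds are also entry criteria, so a rating used for eligibility may regress to the mean. Averaging is therefore a trade-off, not a free gain.

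**Conclusion.** The point holds for the interaction tests. As printed, both interaction models contradict their own interpretation. If the Aim 1 equation is followed, a constant 0.61 SD effect would be labelled as changing over time in roughly 73-89% of trials by chi-square, or 68-85% by F, instead of 5%. Those ranges rest on 27 per arm, r = 0.6 and assumed follow-up correlations of 0.8 down to 0.6. The domain omnibus test has the same structural fault; its size is not computed here because the plan gives no between-domain correlations.

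The tests at risk are the exploratory heterogeneity tests for positive symptoms and cognitive domains, and any corresponding tests for CDS and SANS. When there is no effect at all, the printed term still holds its 5% level. The harm is therefore a misdescribed effect, not a false claim that one exists.

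The undefined baseline score is a separate gap in specification. Averaging the pre-treatment ratings could bring the detectable effect to 0.54-0.60 SD instead of 0.61, or gain nothing, depending on correlations the documents do not give.

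**What to change.** 1. Write the Aim 1 model as follow-up = baseline + week + treatment + treatment x week, and the domain model as follow-up = baseline + domain + treatment + treatment x domain.
2. Define the average treatment effect as the equal-weight mean of the weekly adjusted differences, so that it does not depend on how the week indicators are coded.
3. State that heterogeneity is tested by the (weeks-1)-df contrast of equal effects over weeks, and by the (domains-1)-df contrast for domains. Keep the week 8 contrast as it is.
4. Say that the CDS and SANS models take the same form.
5. State in advance which pre-randomisation rating or ratings form the baseline score, and whether a rating used for eligibility is included. Averaging is optional.

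The cost is wording and a few lines of code. No new data are needed, and the sample size and the primary contrast are unchanged.
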